1.0 Introduction

- Evidence shows that although clinical trials are aimed at producing new strategies for reducing cancer morbidity and mortality, participation remains suboptimal for all populations, especially those from racial and ethnic groups [1-3]. Although some interventions have been found to be effective at enhancing participation, few studies have tested tailored communication activities using innovative communication techniques (perceptual mapping) with aims to address barriers and facilitators for patients and facilitate more engaged discussions with their providers in real world settings. We therefore aim to fill that gap by testing a culturally diverse and patient guided mHealth decision tool called **mychoice**, which allows patients to explore their concerns and questions related to clinical trial participation, as well as create a customized and personalized set of questions to enhance patient-provider communication and increase informed decision making. This study employs a mixed-methods approach using both qualitative and quantitative data to evaluate the effectiveness of the **mychoice** intervention for patients and to explore the provider and organizational factors that impact implementation. A randomized controlled trial will be performed with 270 participants in order to determine the acceptability and feasibility of the intervention, as well as its effects on self-efficacy in discussing clinical trial participation with providers, leading to enhanced informed decision-making. Results will also investigate whether the tool has enhanced effects on minority patients, particularly African Americans. A secondary aim of the study is to evaluate the implementation of the intervention in clinical settings. Implementation evaluation will occur using surveys of medical staff whose patients are participating in the study. These surveys will assess institutional facilitators and barriers to study implementation. We will also conduct cognitive de-briefing interviews after the intervention is completed with key stakeholders at the participating institutions, which will inform a larger implementation study in the future.

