2.0 Objectives

- The **primary objective** of the study is to assess the effectiveness of the **mychoice** mHealth tool on perceived patient self-efficacy and decisional conflict, and whether these results are enhanced in minority patients.
- The **secondary objective** of the study is to describe the acceptability and feasibility of implementing **mychoice** in oncology services at three leading cancer centers in Philadelphia.
- **Purpose of the study:** **mychoice** was conceptualized and developed with a Fox Chase-Temple NODAL grant, using extensive formative research, including the use of commercial marketing techniques (perceptual mapping and vector modeling) and

patient engagement, and customized to address the significant barriers for African American patients to consider clinical trials. The tool went through user testing and received excellent reviews, and now is ready for an efficacy test. This study represents the next step in personalized clinical trial education research. It completes the **mychoice** communication tool to make it multi-cultural and thus appropriate for all patients, and tests its effectiveness with diverse cancer patients to improve knowledge and preparation to discuss clinical trials within real world settings. We will also explore organizational factors that impact implementation of a technology-based intervention, an innovative aspect that will provide critical understanding on feasibility to ensure scalability in a large medical setting. Results could inform how a tool like **mychoice** could be implemented in a cancer center and enhance communication about clinical trials between patients and doctors.

- **Specific Aims:**

- **AIM 1:** Test the perceived usefulness and effectiveness of **mychoice** to increase patients' self-efficacy and decrease decisional conflict.
 - **AIM 2:** Describe the acceptability and feasibility of implementing **mychoice** in oncology services at three leading cancer centers in Philadelphia by identifying provider and organizational factors influencing its integration in the clinical space.
- The following **hypotheses** are proposed for Specific Aim 1:
 - **H1:** Compared to a non-tailored education aid, **mychoice** will improve self-efficacy in making a decision about participating in clinical trials for all patients as well as a subsample of underrepresented patients (non-white).

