4.0 Study Design

a) Recruitment methods

- We will recruit a total of 270 patients (~~100-130~~ at FCCC via the medical oncology, radiation oncology, and surgery units and 100 at TUHS via the cancer center). The remaining ~~40-70~~ patients will be recruited at Thomas Jefferson University Hospital and The University of Pennsylvania We anticipate that approximately 20% of the participant pool will be non-white which should provide sufficient number to perform sub-analyses of effects. We will monitor this during recruitment, however, and if we find that we are not reaching this number of non-white participants, we will change the protocol to focus on recruiting only non-white participants.
- There are three ways that patients will be recruited for the study at FCCC. This is shown in Figure 1.

- (1) First, at FCCC, [name] will collaborate with FCCC oncologists to identify patients who might be offered a clinical trial but who have not participated in a clinical trial previously. A patient information card and a flyer have been developed for oncologists to provide to patients (see

Appendices A and B). Oncologists will suggest the study to patients at regular visits and be instructed to either go to the Resource and Education Center at Fox Chase, or find a study representative in the waiting area at a table who is wearing a mychoice pin. Mychoice study staff will be in the waiting areas of participating oncologists on days/times that are busiest. If staff are not available that day, they can go to the REC. If the patient approaches a study staff, they will meet the patient in a designated private space, consent them, and give them the option of doing the study then on either a provided iPad or go to the REC to do the study on a computer.

- (2) Study staff will also be available in the common areas of FCCC at a table. Patients can come up to the table and ask about the study. We will also have a small “wheel” that is a game that patients can play to win small prizes (candy, umbrella, \$5 gift cards). All patients who come up to the table can play and win a small prize; there is no requirement to enroll in the study to play. If they are interested in the study, we will provide an information card and answer any questions they have. They can then complete consent and do the study then (as above) or have the option to complete the study at home.

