- (3) Another way for patients to participate is through a referral by REC staff. When patients go to the REC, staff will provide information to the patients about the study. If they are interested, REC staff will go through the above steps to consent a patient and provide them an iPad or computer to complete the study.
- (3) The last way for patients to participate will be by self-referral. Cards and posters will be available throughout the waiting areas. On this card are the study email and phone number. Patients could use these to contact study staff who will explain the study and verbally consent people over the phone and then provide the option to come to do the study at home or at the REC. Because this consent is occurring over the phone, staff will use a script (provided) to explain the study and screen for eligibility. A waiver of document of consent has been provided to assist with this process. After they have verbally been consented for the study, they will be sent a link to the study through the RedCAP system and provided information on how to complete the study. They will be directed to review the study consent and indicate their willingness to participate by entering their name as an e-signature. They then will be asked to do the same with the HIPAA waiver. Once they agree, they will be directed to the baseline survey.
- Patients recruited at TUH, Jefferson, and HUP will follow the same recruitment strategies, but will only be recruited by Physician Referral and Self-Referral. There are no REC staff at these institutions, so recruitment strategies will rely solely on study staff and physicians. Study staff will be in the waiting rooms prepared for any referrals during busy clinic days.

[figure not shown]
- All study materials, including the pre and posttest and the patient education materials, are programmed in REDCap. If completing the study in person, once the patient agrees to be in the study and is set up in the RedCAP system, study staff will explain this process and have them sign in the REDCap system to indicate they agree to participate (script for staff to follow in Appendix C) and to the HIPAA waiver. Study assignment will be random and programmed into the system

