Experience with clinical trial discussions		Self-reported experience about clinical trial discussions with provider (6 items)			X
Satisfaction with Decision	Enswistle, et al	Satisfaction with decision about clinical trials (6 items)			X

To assess implementation issues and address Specific Aim 2, we will use the Consolidated Framework for Implementation Research (CFIR) to guide the implementation evaluation, focusing on the acceptability and feasibility of implementing the *mychoice* study as well as the integration of this tool in ongoing practice. This evaluation is descriptive in nature. To evaluate the acceptability and feasibility of the proposed *mychoice* study, we will collect data from the initial planning meetings, review of recruitment logs and files, as well as surveys from physicians who have patients that are participating in the study. Meeting notes will be kept and used to design the recruitment process, procedures, and logs. Prior to the start of recruitment (using REDCap; Appendix H) and at project end (will be developed based on how intervention is implemented in sites), an online survey will be conducted with each physician who has patients who are participating in the study. The survey will assess level of commitment to the project and potential barriers. The survey will include key constructs from CFIR, such as perceptions of intervention strength, relative advantage, trialability, patient needs, self-efficacy, and champions. During the recruitment period and throughout the study, recruiters will keep logs of the number of identified patients, number of consented patients, and notes regarding challenges and opportunities in the recruitment process. At the end of the recruitment, the PIs will conduct debriefing interviews with the stakeholders (guide to be developed based on implementation) at each site to more fully explore the challenges and opportunities for ongoing implementation and sustainability (Figure 3). Table 2 describes the measures for the implementation evaluation.

Figure 3. Implementation Process Study Design

[figure not shown]

Table 2. Implementation Constructs

CFIR Constructs	Baseline Survey	End of Study	Debrief Interviews	Meeting Notes
I. Intervention Characteristics				
Source	X	X		
Evidence Strength & Quality	X	X	X	X
Relative Advantage	X	X	X	X
Complexity	X	X	X	X
II. Outer Setting				
Needs & Resources of Those Served by the Organization	X	X	X	X
III. Inner Setting				
Culture	X	X		
Implementation Climate	X	X	X	X

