Tension for Change	X	X		
Readiness for Implementation	X	X		
Leadership Engagement	X	X		
Available Resources	X	X		
IV. Characteristics of Individuals				
Knowledge & Beliefs about the Innovation	X	X	X	X
Self-Efficacy	X	X	X	X
V. Process				
Planning			X	X
Engaging			X	X
Formally Appointed Internal Implementation Leaders			X	X
Champions			X	X
Key Stakeholders			X	X
Executing			X	X
Reflecting & Evaluating			X	X

- **Timeline: This is a 33 month project (4/2017-12/2019)**

		12/17	6/18	7/19	12/19
Months:	1-6	1-9	10-15	16-28	29-33
Revisions based on initial user testing	X	X			
Review by key stakeholders	X	X			
New patient testimonials to increase diversity	X				
Final Production	X	X			
Create Study Instruments		X			
Finalize data management system		X	X		
Recruitment process established at sites					
1. Fox Chase			X		
2. Temple			X		
3. Jefferson				X	
4. Penn				X	
IRB review and approval at study sites					
1. Fox Chase			X		
2. Temple			X		
3. Jefferson				X	
4. Penn				X	
Recruit 270 Patients				X	
Conduct pre-intervention implementation surveys with participating staff				X	
Conduct baseline, intervention, and post test				X	
Conduct one-month follow-up surveys				X	
Conduct post intervention implementation surveys				X	
Data Analysis – Patient Surveys					X
Tracking analysis-metrics in mychoice					X

In-depth implementation interviews with site stakeholders					X
---	--	--	--	--	---

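### The physician survey for Aim 2 is restricted to physicians with participating patients, a rule that cannot be applied before recruitment and that at project end leaves out those with no enrolled patient

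*Combined protocol and SAP*

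**What the plan says.** Aim 2 (section 2.0) is to describe acceptability and feasibility by "identifying provider and organizational factors influencing its integration in the clinical space". The physician survey is one of its data sources.

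The documents restrict the respondents to those with participating patients in three places:

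- Section 1.0: "Implementation evaluation will occur using surveys of medical staff whose patients are participating in the study".
- Section 4.0, in the list of Aim 2 data sources: "as well as surveys from physicians who have patients that are participating in the study".
- Section 4.0, in the survey description itself: "an online survey will be conducted with each physician who has patients who are participating in the study".

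The survey is timed "Prior to the start of recruitment (using REDCap; Appendix H) and at project end", and the same sentence sets both the timing and the respondents, so the restriction covers both waves.

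The timeline in section 4.0 describes the first wave differently: "Conduct pre-intervention implementation surveys with participating staff". As the table was extracted, that row is marked in the same column, months 16 to 28, as patient recruitment.

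Nowhere do the documents say that physicians who were approached but had no enrolled patient will be surveyed.

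**The concern.** A survey needs a list of people that exists when the survey is sent. Here membership depends on patient enrolment, which has not happened at the first wave and is itself a product of implementation by the second.

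The second wave matters more. Aim 2 looks for what helps or hinders use of the tool in clinics. A physician who was asked to refer and ended with no enrolled patient may have met exactly the barriers the aim is looking for, yet falls outside the rule. Referral by physicians carries particular weight at Temple, Jefferson and Penn, where section 4.0 allows only physician referral and self-referral.

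At stake are the survey's description of barriers, its response-rate denominator, and any informal reading of the two waves side by side if they reach different people.

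**Working it through.** The plan gives no number of physicians, no response target and no sample size for Aim 2, so there is no figure to reproduce. The check sets the texts side by side, then counts constructs, then shows how the bias would behave.

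**1. Can the rule be applied at each wave?**

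- Before recruitment, no patient is in the study, so the set of physicians with a participating patient is empty.
- At project end, the set is defined, but it excludes every approached physician with no enrolled patient.

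**2. Do other Aim 2 sources cover the gap?** Table 2 marks 13 constructs under the baseline and end-of-study surveys.

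- Seven are also marked under debrief interviews and meeting notes: evidence strength, relative advantage, complexity, needs and resources of those served, implementation climate, knowledge and beliefs, and self-efficacy.
- Six are marked under the surveys only: source, culture, tension for change, readiness for implementation, leadership engagement and available resources. Check: 13 − 7 = 6.

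Several of the six are organisational factors of the kind Aim 2 names. The recruitment logs count identified and consented patients and hold recruiters' notes; they do not collect physicians' ratings of these constructs.

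**3. How would the bias behave?** Let s be the share of approached physicians with no enrolled patient, pE the share of favourable answers among physicians with enrolled patients, and pN the share among those without. With full response, the planned survey reports pE, while the value over all approached physicians is (1 − s)·pE + s·pN. Hence

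bias = pE − [(1 − s)·pE + s·pN] = s × (pE − pN).

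Every input below is an assumption; none comes from the documents. Results are in percentage points.

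| pE | pN | s = 10% | s = 30% | s = 50% |
|---|---|---|---|---|
| 80% | 40% | +4 | +12 | +20 |
| 80% | 60% | +2 | +6 | +10 |
| 80% | 80% | 0 | 0 | 0 |
| 70% | 80% | −1 | −3 | −5 |

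For example, 0.30 × (80 − 40) = 12. The sign depends entirely on whether pN is below pE, which is plausible but not documented.

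**The case against.** The strongest reply is that the wording is loose and the intention clear. Section 4.0 says "Mychoice study staff will be in the waiting areas of participating oncologists on days/times that are busiest", and the timeline speaks of participating staff. Read together, the first wave may be meant for physicians who agreed to take part. Figure 3 and the physician questionnaire (Appendix H) are not in the text available, so a list defined there cannot be excluded. This stands in part: a reader might infer that the baseline survey is impossible, but that is true only of the literal rule. The text never ties the participating oncologists to the survey, however, so a site could not build its list from it.

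A reader might also infer that only physicians for whom the tool worked are surveyed. The documents do not support this. Randomisation is 1:1, so about half of participants receive the control material. A physician need not refer anyone to have a participating patient: "The last way for patients to participate will be by self-referral", and at Fox Chase patients also enter through tables and the resource centre. Some physicians who never referred therefore stay in the survey.

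Nor do the documents show that Aim 2 will overstate feasibility. Logs are compared with recruitment goals, and the meeting notes and stakeholder interviews are not limited to physicians with enrolled patients. These sources could reveal failed recruitment. They do not reach the six survey-only constructs, and the stakeholders are not defined as including physicians without enrolled patients.

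Finally, it is tempting to say that a before-after comparison is invalidated. The plan contains none: the evaluation is descriptive, and the end survey is still to be written. Different respondents at the two waves would limit interpretation, not break a planned analysis.

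**Conclusion.** The point holds in a limited form. The stated rule cannot be applied literally before recruitment, conflicts with the term in the timeline, and at project end selects physicians by whether a patient enrolled. The end survey may therefore describe provider and organisational barriers too favourably, chiefly for the 6 of 13 surveyed constructs that have no interview or meeting-note source.

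The upward direction rests on the assumption that physicians without enrolled patients are less favourable. If the two groups hold the same views the bias is zero, and if the assumption is wrong it reverses. No size can be derived from the documents. The count of six rests on Table 2 as extracted, and the conclusion on there being no separate list in the figure or appendix that could not be read.

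Aim 2 is secondary and descriptive, and the Aim 1 comparison is untouched. The change is still worth making, because it is cheap and the views of physicians left out may not be recoverable after the study closes.

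**What to change.** - Before recruitment, fix a list at each site of all physicians who are asked to refer or whose clinics are used for recruitment.
- Send both the baseline and the end survey to that list, whether or not the physicians' patients enrol.
- Report response rates and results separately for physicians with and without an enrolled patient.
- Reconcile the descriptions of the respondents in section 1.0, in the two places in section 4.0, and in the timeline, and make clear that the first wave precedes recruitment at each site.

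The cost is a short text change and a few more email surveys, each of which section 8.0 puts at under 5 minutes. The main downside is a probably lower response rate among physicians without enrolled patients. Some selection would then remain, but it would be visible in the reported rates.

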5.0 Risks to Participants

- Participating in this study does not pose direct physical risk to patients. Participants may have questions about clinical trials after taking the surveys, in which case they will be instructed to talk with their oncologist about medical or eligibility questions related to clinical trials. Participants may also be directed to the Resource and Education Centers at TUHS for additional information about clinical trials.

6.0 Potential Benefits to Participants

- Participating in the study does not pose direct physical benefit to participants. This is not a therapeutic study, but rather an evaluation of an educational app. The results of the research will be used to modify the app thereby making it a more appropriate and useful decision-making tool to help African American, and other cancer patients, make better informed decisions concerning clinical trial participation.

7.0 Provisions to Maintain the Confidentiality of Data

- All information collected for this study will be kept confidential. Subjects will be told that all information will be kept in strict confidence. All deidentified survey data will be downloaded from RedCAP and stored on computer files or in locked filing cabinets to which only select members of the research staff will have access.
- RedCAP survey data and user data from the mHealth tool will be identified only by participant number and will be downloaded into SAS for analysis.
- ipads have been purchased for this study and will be used to implement the intervention, along with computers used either at the REC or in the participant’s home. All ipads and REC computers are password protected with only study staff having that information. No files will be saved or downloaded on the ipads or computers, and no data will be accessible on the ipads or computers that would identify patients. Participants will go to a RedCAP study URL which will then randomize them to condition. All data from the surveys will be gathered by the RedCAP system and not on the ipad or computer itself.
- All participating sites will direct patients to the RedCAP URL to begin the study. No data will be shared with them and they will not have access to the data. Only study PIs and the study coordinator will have this access.
- For medical staff personnel, surveys will also be sent via email where they will be provided a RedCAP link. When conducting interviews, a digital recorder will be used to capture the interview. These will be transcribed and then destroyed. No identifying information will be recorded on the transcriptions.

- All data will be housed behind the firewall at Fox Chase Cancer Center using RedCAP. The PIs and study coordinator, will have access to this data and will download de-identified data for analysis to share with the biostatistician to be used in SAS. A special study ID and password will be required to enter into RedCAP. In addition, any additional files will be password protected and kept on secure, fire-wall protected servers at Temple University and Fox Chase Cancer Center .

